Functional recovery of renal function from acute renal failure occurs in 75% of patients at approximately 14 days after onset of the disease (Schrier, Diseases of the Kidney). In liver transplantation, intraoperative hemodynamic insults typically lead to acute renal failure which may be further worsened by exposure to CNI therapy in the early postoperative period. In practice, patients who demonstrate early evidence of acute renal failure often have their CNI therapy delayed for 4-5 days. This duration of CNI delay is too short to have any salutary effect on the

course or severity of acute kidney injury as less than 20% of patients experience any functional recovery by day 5.

Thymoglobulin® (Sanofi, Cambridge, MA) is a polyclonal immunosuppressive agent that is derived from rabbits immunized with pediatric thymocytes. It contains antibodies to a wide variety of T-cell antigens and MHC antigens and is approved for the treatment of kidney rejection by the Food and Drug Administration (FDA) in the United States. Thymoglobulin® has been shown to be a safe and efficacious induction therapy that permits delayed exposure to CNI therapy while preventing the occurrence of acute rejection in kidney transplantation.^{42, 43} We hypothesize that any perioperative insult leading to AKI in OLT recipients is unlikely to be beneficially impacted by a short delay of CNI introduction. We further hypothesize that avoidance of CNI for 10 days will have a beneficial effect on the course and severity of perioperative AKI. Since perioperative AKI is a potent risk factor for CKD in the late post-transplant period, we hypothesize that minimizing the risk and severity of AKI with prolonged delayed exposure to CNI will have a beneficial effect on renal function late after liver transplantation.

INVESTIGATIONAL AGENT – [ANTI-THYMOCYTE GLOBULIN (RABBIT)] – r-ATG THYMOGLOBULIN®:

A. Chemistry

Thymoglobulin® (anti-thymocyte globulin [rabbit]) is a purified, pasteurized, gamma immunoglobulin, obtained by immunization of rabbits with human thymocytes (*Thymoglobulin® Prescribing Information*). This immunosuppressive product, a polyclonal antibody, contains cytotoxic antibodies of defined specificity against functional molecules on T-lymphocytes. Thymoglobulin® is supplied as a sterile, freeze-dried product for intravenous administration after reconstitution with a diluent, (Sterile Water for Injection, United States Pharmacopeia [USP]).

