Tacrolimus will be administered to all subjects according to the protocol-specified dosing regimen, [to maintain Tacrolimus Blood Trough (C-0h) Levels/Concentrations] shown in **Table 4**. Tacrolimus to be administered by mouth or through the NG tube [suspension] if not able to take by mouth. In rare cases, better if not, could be administered as sublingual. We should try not to use tacrolimus as intravenous unless absolutely necessary.

Table 4:

Tacrolimus Blood Trough (C-0h) Levels / Concentration-Guided Dosing Regimen		
	Group 2 / Arm 1 Thymoglobulin® / Delayed CNI Group	Group 2 / Arm 2 Early CNI Group
Day(s) Post OLT	Blood Trough C-0h Level	Blood Trough C-0h Level
Day(s) 0-10	N/A – No CNI permitted	≥ 8 ng/mL and ≤ 12 ng/mL
Day(s) 10-30	≥ 6 ng/mL and ≤ 12 ng/mL	≥ 6 ng/mL and ≤ 12 ng/mL
Day(s) 31-60	≥ 6 ng/mL and ≤ 10 ng/mL	≥ 6ng/mL and ≤ 10ng/mL
Day(s) 61-90	≥ 5 ng/mL and ≤ 8 ng/mL	≥ 5 ng/mL and ≤ 8 ng/mL
Day(s) 91-179	≥ 5 ng/mL and ≤ 8 ng/mL	≥ 5 ng/mL and ≤ 8 ng/mL
Day(s) 180+	≥ 3 ng/mL and ≤ 8 ng/mL	≥ 3 ng/mL and ≤ 8 ng/mL

In the event of CNI intolerance, (e.g. **nephrotoxicity**), dose reduction of tacrolimus may be necessary. The tacrolimus dose may be adjusted as needed by Investigator. All dose adjustments/modifications will be recorded on the appropriate CRF page, at each Study Visit.

In the event of **neurotoxicity, due to tacrolimus**, the patient will be switched over to **cyclosporine** as the **CNI alternative**. In this event the patient will not need to be removed from the study. This change in CNI, (from tacrolimus to cyclosporine), will be recorded on the appropriate CRF.

Cyclosporine (CsA) will be administered to maintain Cyclosporine Blood Trough (C-0h) Levels/Concentrations shown in **Table 5**.

Table5:

Cyclosporine (CsA) Blood Trough (C-0h) Levels / Concentration-Guided Dosing Regimen		
	Group 2 / Arm 1 Thymoglobulin®/Delayed CNI Group	Group 2 / Arm 2 Early CNI Group
Day(s) Post OLT	Blood Trough C-0h Level	Blood Trough C-0h Level
Day(s) 0-10	N/A – No CNI permitted	≥ 200 ng/mL and ≤ 300 ng/mL
Day(s) 10-30	≥ 150 ng/mL and ≤ 250 ng/mL	≥ 150 ng/mL and ≤ 250 ng/mL
Day(s) 31-60	≥ 150 ng/mL and ≤ 200 ng/mL	≥ 150 ng/mL and ≤ 200 ng/mL
Day(s) 61-90	≥ 100 ng/mL and ≤ 200 ng/mL	≥ 100 ng/mL and ≤ 200 ng/mL
Day(s) 91-179	≥ 100 ng/mL and ≤ 150 ng/mL	≥ 100 ng/mL and ≤ 150 ng/mL
Day(s) 180+	≥ 100 ng/mL and ≤ 150 ng/mL	≥ 100 ng/mL and ≤ 150 ng/mL

B. Corticosteroids:

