from the study. Information will be collected on serum creatinine levels, urea, eGFR, rejection episodes, graft loss/re-transplant, malignancies, opportunistic infections, patient survival and immunosuppressive therapy.

Subjects who did not complete the planned Thymoglobulin® course will be followed for any SAE(s) occurring within 30 days following the last dose of Thymoglobulin®. **These SAE(s) will be reported on the (MedWatch SAE Form) and UPLOADED to the Sanofi PV Portal, and faxed to Cleveland Clinic PI – “Attention: [name]” at [contact], within 24 hours of Study Site discovery/notification.** Since subjects will be followed even after discontinuation of the Study Drug, the **Study Completion CRF** should only be completed at 30 days, and Month 12 or earlier if the subject can no longer be followed. The following reasons are potential causes for premature discontinuation of study: graft loss, death, lost to follow-up and withdrawal of consent.

I. Emergency Un-Blinding of Treatment Assignment

This is an open-label study.

J. Study Completion and Post-Study Treatment

A Study Completion CRF should be completed at Month 12. The Investigator also must provide follow-up medical care for all patients who are prematurely withdrawn from the study, or must refer them for appropriate ongoing care. In addition, investigators will be asked to provide, for each randomized patient, a one-year follow-up data to describe patient survival, graft survival, acute rejection, current immunosuppressive regimen, recurrence of hepatitis C and renal function.

EFFICACY AND SAFETY ASSESSMENTS:

A. Renal function

Renal function will be assessed by estimated Glomerular Filtration Rate (eGFR), using the MDRD 4-variable equation. Serum creatinine will also be used as a parameter for determination of renal function at each Study Visit. Subjects will be classified for each occurrence of AKI according to the criteria in **Table 2**. Serum creatinine and weight must be recorded on the Study Visit CRF. All subjects will have their eGFR assessed at baseline, **Month 1, 3, 6, 9 and Month 12 post-transplant.**

B. Acute Cellular Rejection

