Designated Study Personnel, (at each Study Site), must enter the information required by the protocol onto the paper Case Report Forms (CRFs). The information from the paper CRFs will then be entered directly into the electronic Database, REDCAP, by designated Study personnel at each Study Site. Edit checks and double data entry with verification upon second entry are built

into specific data items. Text items (e.g. comments) are entered once. Queries are sent to the investigational site using an electronic data query. Designated investigational Study Site staff will be required to respond to all queries and make any necessary changes to the data. Other errors or omissions are entered on Data Query Forms, which are made accessible to the investigational site for resolution.

Concomitant medications entered into the database will be coded using the WHO Drug Reference List which employs the Anatomical Therapeutic Chemical classification system. Coexistent diseases and Adverse Events (AEs) will be coded using the Medical dictionary for regulatory activities (MedDRA) terminology.

D. Handling of Missing Values/Censoring/Discontinuations

Since the study subjects will be followed for renal function, graft loss, or survival status, the subjects with missing measurements at 30 days will only be those who die, withdraw consent or are lost to follow-up. It is expected there will be very few such patients within 30 days. Missing values at day 30 will be imputed using the last observation carried forward (LOCF) approach. Missing baseline serum creatinine values will be replaced with the most recent available value from the pre-transplant period.

STUDY ENDPOINTS / EFFICACY AND SAFETY

A. Primary Endpoints:

Efficacy and Safety (Primary):

Primary Efficacy and Safety variables to be evaluated at 30 Days Post Liver Transplant are:

- Incidence of AKI
- Serum creatinine and eGFR

B. Secondary Endpoints:

Efficacy and Safety (Secondary):

Secondary Efficacy and Safety variables to be evaluated at 30 Days Post Liver Transplant are:

- The incidences of acute cellular rejection, (ACR), at 30 days post-transplant.
- Patient survival at 6 months post-transplant.
- Graft survival at 6 months post-transplant.
- Incidence of AEs / SAEs

C. Additional Efficacy and Safety Variables for Evaluation:

- Patient survival at 12 months post-transplant
- Graft survival at 12 months post-transplant

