I = Liver Biopsy to be performed as clinically indicated, (for confirmation of suspected ACR and/or HCV infection recurrence), and per Investigative Site standard liver transplant protocol. For suspected ACR, Liver Biopsy MUST be performed PRIOR to the initiation of anti-rejection therapy.

J = PT/INR on Day (-1) or Day 0 (prior to liver transplant), and post liver transplant per Investigative Site liver transplant protocol.

K = Randomization to take place within 6 hours of completion of OLT and arrival in ICU.

L = Day (-1) or 0 [Pre OLT]; Day 10, Month(s) 1, 3, 6, 9, and 12 post LT, and per Investigative Site Liver Transplant Protocol.

M = Day 10; Month(s) 1, 3, 6, 9, and 12, and per Investigative Site Liver Transplant Protocol.

N = Month(s) 1, 3, 6, 9, and 12.

O = Serum or Urine pregnancy test to be performed on Day (-1) or Day 0 (prior to OLT), on all Women of Child Bearing Potential (WOCBP). Urine pregnancy test to be performed, (at Day 10, Month 3, and Month 12) post LT Visits, on all Women of Child Bearing Potential (WOCBP).

P = All AE(s)/SAE(s) will be reported from randomization till 30 days after study completion. Any SAE occurring after patient randomization, until 30 days after the patient has stopped study participation, must be reported. In addition, for patients who are withdrawn from study participation “early”, SAEs are to be reported for up to 12 months after the date of patient randomization, if a relationship to the study is “suspected”.

R = Per Investigative Site Liver Transplant Protocol.

S = For patients who are HCV “Negative” – per Investigative Site Liver Transplant Protocol. For patients who are HCV “Positive” – HCV RNA (quantitative levels) are to be drawn on Day (-1) or Day 0 (pre-OLT), at Week 1, Month(s) 1, 3, 6, 9, and 12 (post OLT), in order to follow the patient’s HCV response to Thymoglobulin.

T = r-ATG Infusion will be administered to subjects randomized to Arm 1 ONLY, on Day 0 (after OLT) within 12 hours of arrival in ICU, on Day 2 and Day 4 Post OLT.

U = CNI blood trough levels to be performed beginning day after initial dose of CNI and as per Investigative Site Liver Transplant Protocol, (as per clinically indicated), and at Month(s) 1, 3, 6, 9, and 12 Visits.

V = In case of early discharge after liver transplant these clinic visits and clinical data can be excluded however, immunosuppressive regimen and blood work results should be collected and recorded.

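### LOCF gives patients who die before Day 30 a Day-30 creatinine and eGFR taken before death; the likely effect is small and the repair is cheap

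*Combined protocol and SAP*

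**What the plan says.** The section on missing values (Data Collection, Quality Assurance, and Management, part D) states that "the subjects with missing measurements at 30 days will only be those who die, withdraw consent or are lost to follow-up", adds that "It is expected there will be very few such patients within 30 days", and then gives one rule: "Missing values at day 30 will be imputed using the last observation carried forward (LOCF) approach". It makes no exception for death, and no sensitivity analysis is planned there or in the endpoint section.

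Serum creatinine and eGFR at 30 days are listed as primary in the Synopsis, the Investigational Plan and the Study Endpoints section. The Investigational Plan also calls AKI stage 2 to 3 the primary endpoint. The sample size rests on change in creatinine, compared by Welch's t-test.

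On data available to carry forward:
- The renal function section says "Serum creatinine and weight must be recorded on the Study Visit CRF".
- Appendix A, footnote L, sets the chemistry schedule: "Day (-1) or 0 [Pre OLT]; Day 10, Month(s) 1, 3, 6, 9, and 12 post LT", plus tests under each site's own protocol. Footnote M does the same for eGFR.
- Footnote V says that, after early discharge, "immunosuppressive regimen and blood work results should be collected and recorded".

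On CNI exposure, Table 4 has "No CNI permitted" for Arm 1 in Days 0 to 10. Table 1 starts Arm 2 within 48 hours of transplant.

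**The concern.** A patient who has died has no renal function at Day 30. The rule gives that patient a number anyway and averages it with the survivors' measured values.

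The carried number is also not neutral between arms. If it comes from about Day 10, it was taken before or at the start of CNI in Arm 1 and after about 8 days of CNI in Arm 2 (Day 10 minus Day 2). CNI exposure is the factor under test. The value may also precede recovery: the Study Rationale says "Functional recovery of renal function from acute renal failure occurs in 75% of patients at approximately 14 days after onset of the disease". Or it may come from a laboratory test close to death, or from before a later decline. It can therefore be too high or too low.

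At stake are the mean difference and the precision of two listed primary variables, with nothing planned that would show the effect.

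**Working it through.** **1. The plan's own figure.** Inputs from the sample-size section: difference 0.32 (no unit stated; mg/dL assumed), SD 0.51 in both arms, two-sided 5%, 55 per arm. Welch power from the noncentral t is 90.3%, so the stated 110 patients for 90% power is reproduced.

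**2. How many deaths by Day 30.** The plan gives no number. Its background sections give three guides:
- 298-patient retrospective series, 1-month survival 81% (59 patients with abnormal renal function) and 96% (239 with normal function): (59 × 19% + 239 × 4%) / 298 = 7.0%; × 55 = 3.8 per arm.
- RIFLE-based series, 30-day survival 95.7%, 91.2% and 76.3%, with 11.1% and 25.7% in the two raised-creatinine groups: 0.632 × 4.3% + 0.111 × 8.8% + 0.257 × 23.7% = 9.8%; × 55 = 5.4 per arm. This assumes that the remaining 63.2% have normal-function survival.
- Normal-function group of the 298-patient series alone: 4% × 55 = 2.2 per arm.

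That is roughly 2 to 5 per arm. It is not a floor. The trial excludes MELD above 34 and RRT at transplant, and it randomises only after ICU arrival.

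**3. Shift in the mean difference (illustration; distances assumed).** With a net excess of k deaths in one arm, each carrying a value D from the survivors' mean, the shift is k × D / 55.
- k = 1, D = 1 mg/dL: 1/55 = 0.018, or 6% of 0.32.
- k = 3, D = 1 mg/dL: 3/55 = 0.055, or 17% of 0.32.

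The shift can go either way. It is near zero if deaths and carried values are balanced.

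**4. Loss of precision when deaths are balanced.** Simulated Welch tests use 55 per arm, with 3 carried values per arm lying D above that arm's own mean. The comparator leaves the 3 deaths out (52 per arm).

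| Handling of 3 deaths per arm | Power |
|---|---|
| Left out | 88.7% |
| LOCF, D = +0.5 mg/dL | about 89.5% |
| LOCF, D = +1 mg/dL | about 86% to 87% |

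Steps 3 and 4 use planning inputs for delta creatinine that are not stated to be Day-30 figures.

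**5. Reach of the rule.** The LOCF sentence covers all missing Day-30 values and is not confined to creatinine and eGFR. The Investigational Plan defines AKI at 30 days without saying whether this means any episode through Day 30 or status on that day. The renal function section, which classifies each occurrence of AKI, points to the first reading but does not settle it. Under the second, LOCF also reaches the AKI endpoint.

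**The case against.** The strongest reply is that this is a small matter. The plan expects very few missing patients, and its hypothesis is that survival is similar in the two arms. Creatinine is recorded at every study visit and sites run their own tests, so a carried value will usually exist and may be later than Day 10. At +0.5 mg/dL, keeping deaths by LOCF costs no power against leaving them out. All of this stands, and it limits the size of the point. It does not answer the question of meaning, because a pre-death value is still counted as Day-30 renal function.

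A second reply is that comparing survivors conditions on an event after randomisation, one that the Introduction itself ties to renal failure. That is correct, and it is why a sensitivity analysis keeping all randomised patients is needed.

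A reader might also infer that the missing rule for creatinine or eGFR measured on RRT undermines the primary comparison. The documents do not support that. Such a patient has a measured value, so LOCF does not apply, and the default is to analyse it as measured. The Table 2 footnote already counts RRT as stage 3 for AKI. The number on RRT at Day 30 is not given. This is a point to clarify only.

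**Conclusion.** The gap is certain from the text: deaths before Day 30 are imputed by LOCF into two listed primary variables, with no exception and no sensitivity analysis. The size is uncertain and probably small: a shift of about 0.02 to 0.05 mg/dL for a net imbalance of 1 to 3 deaths at 1 mg/dL, and a loss of about 2 points of power for 3 balanced deaths per arm at that distance. These figures rest on assumed death counts and distances.

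Two stronger readings should be resisted. One is that LOCF favours a particular arm: the carried value may be too high or too low, so the direction is not determined. The other is that power collapses. Simulated power does fall to about 73% and 49% with 3 deaths per arm at +2 and +3 mg/dL, but every carried value would have to lie that far out, and no section gives such distances.

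Nor can AKI be declared unaffected until its 30-day definition is settled. The point should be fixed, but it does not threaten the trial's validity.

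**What to change.** In the missing-values section:
- State that LOCF is not used for patients who die before Day 30.
- Make the main comparison in patients alive at Day 30, using change in creatinine from baseline (the variable used for sizing) and eGFR.
- Pre-specify one sensitivity analysis in all randomised patients: a worst-rank Wilcoxon test with death ranked worst and RRT at Day 30 next. Keep the current LOCF analysis as a further one.
- Report by arm the numbers dead, on RRT at Day 30 and imputed, and flag values measured on RRT.
- State that AKI counts any stage 2 to 3 episode through Day 30, or apply the same death rule to it.

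Multiple imputation for the few withdrawals or losses is optional.

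The cost is a paragraph of text and modest programming on data already collected. Under the planning inputs (0.32, SD 0.51), the survivor comparison has about 89% power with 3 deaths per arm (52 left) and 87% with 6 (49 left), against 90% with none. The worst-rank analysis has less, about 83% and 74% by simulation, so it serves as a check on the survivor comparison and not as its replacement.

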C. Number of Patients: One hundred and ten (110) liver transplant recipients will be enrolled in this study, **approximately** 40-50 patients at Cleveland Clinic, (the lead center), and 15-25 patients at each of the three additional participating centers (number of enrollment may vary at different centers).

Sample size estimates for study of liver dysfunction

Sample sizes were computed on the bases of using Welch’s two-sample t-tests to compare changes in creatinine between the control and the thymo 4.5 groups. Assumptions regarding differences in means and standard deviations for each group were based on the results of preliminary data and are given in Table 3. The smaller of the two standard deviations was varied along a range from that observed in the preliminary data to being equal to the larger standard deviation. The former would tend to yield smaller sample sizes, while the latter larger. Assuming that 10% of the patients that are initially enrolled will drop-out before 12 months values are measured, the sample sizes indicated should be increased by 10% to account for this drop-out.

These calculations were done using SAS software (version 9.3, Cary, NC). A significance level of 5% and two-tailed tests were assumed for all testing.

For delta creatinine, we are assuming a difference in means between groups of 0.32. In the pilot data delta creatinine in the control group had a standard deviation of 0.51, while the thymo 4.5 group a standard deviation of 0.12. Therefore, three levels of standard deviation—0.12, 0.32, and 0.51. Based on these calculations, enrolling enough patients to meet the sample size requirements for detecting differences in delta creatinine (within 2 SD, 0.32) will mean having ample sample size for detecting differences in month 12 GFR. Accordingly, we noticed that a sample size of 110 (55 in each group) would give us 90% power with the safest margin for 10% dropouts throughout the study.

Table 3. Minimum sample sizes need to achieve desired levels of power

Comparison	Difference	SD1	SD2	Power	
				80%	90%
Delta Creatinine	0.32	0.51	0.12	46	60
			0.32	58	78
			0.51	82	110
Month 12 GFR	36.8	26.6	20.5	16	20
			23	18	22
			26.6	20	26

D. Selection of Study Population:

INCLUSION CRITERIA

- Patients undergoing deceased donor solitary liver transplantation.
- Age 18 – 75 years at the time of transplantation.
- Willingness and ability to comply with the study procedures.
- Signed Informed Consent Form.

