If Early Patient Withdrawal occurs, or if the subject fails to return for scheduled study visits, the investigator must determine and document which of the above reasons led to the patient's premature withdrawal. For subjects who are lost to follow-up, the investigator should show "due diligence" by documenting in the source documents steps taken to contact the patient, [e.g. date(s) along with documentation of telephone calls, registered letter(s), etc]. Subjects who are prematurely withdrawn from study medication or from the study will not be replaced. Withdrawal of a subject from study treatment does not imply that the subject is withdrawn from the study.

H. Discontinued Subjects

The investigator should accept only those subjects who give a reasonable indication that they will complete the study and comply with study procedures. An evaluation that reflects the status of the subject at premature termination, with a final assessment and reason(s) for termination, must be documented. No replacements will be allowed for treated subjects who do not complete the study.

STUDY TREATMENTS:

A. Investigational and Control Drugs

The administration of Thymoglobulin®, to allow for delayed initiation of CNI, is the Investigational Treatment of the study. It will be administered only to those subjects randomized to Group 1/Arm 1, the delayed CNI group/arm. Subjects randomized to Group 2, the early CNI treatment group/arm will not receive any placebo therapy. The dosing of Thymoglobulin® will be a total of 4.5 mg/Kg, administered as 1.5 mg/Kg/dose, in 3 divided doses.

All Thymoglobulin® infusions will be administered through **a central IV line, via a volumetric infusion pump, through a 0.22 micron filter**. The first dose of Thymoglobulin® will be infused over 6-12 hours, on Day 0, after liver transplantation, **(within 12 hours after arrival to the Intensive Care Unit)**. The subsequent two (2) additional doses of Thymoglobulin® will be infused over 4-6 hours (each dose), on Day 2 and Day 4 post LT.

Subjects are to receive pre-medications, (according to the antibody infusion protocols of each investigative center), [e.g. corticosteroids, anti-histamine, and acetaminophen], to minimize infusion related events.

A total of 110 subjects will be randomly assigned to one of two Treatment Groups/Arms, in a 1:1 ratio, (55 subjects per Group/Arm).

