- Biopsy-proven acute allograft rejection rates at 6 Months and 12 Months post-transplant.
- AKI (Stage 3 rates) at 3 Months post-transplant
- Renal function measured by eGFR at 12 Months post-transplant
- Microbiologically-proven systemic infection rates at 6 Months and 12 Months post-transplant
- Hepatitis C viral loads (in HCV positive recipients) at 12 Months post-transplant
- Incidence of biopsy proven recurrence of HCV infection at 12 Months post-transplant
- Incidence of AEs and SAEs at 12 months post-transplant

For each efficacy event, simple event rate estimates (proportion of events) at 12 months will be obtained, and event rates between the two treatment groups will be compared using Z-statistic based, two-sided, 95% confidence interval for RC – RE, where RC and RE are the event rates for the Early CNI treated Control Group and the Late CNI Initiated/Thymoglobulin® Study Group, respectively. In addition, for the composite efficacy endpoint and its components, individually, Kaplan-Meier survival methods will be used to estimate probabilities of efficacy events by visit. Greenwood’s formula will be used to estimate standard errors and to derive the two-sided, 95% confidence interval of RC – RE, by visit window. HCV replication in HCV positive patients will be compared with summary statistics.

Due to the short duration of study involvement, we expect very few patients to be lost to follow-up, or to withdraw consent. Therefore, for the composite efficacy endpoint, patients who are discontinued from the study for these two reasons, (prior to the incidence of death, graft loss, or biopsy-proven acute cellular rejection), will not be considered as efficacy failures. If there are an adequate number of subjects from each clinical center, a formal test of center by treatment interaction effect will be made.

Adverse Events (AEs) / Infections:

Generally, infections are analyzed together with Adverse Event data. **In addition, infections will be analyzed separately. Infections will be documented on both, the Infection CRF and the AE CRF.** The data collected on both CRFs will be coded with the MedDRA dictionary which gives preferred term and body system information.

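### The Z-based and Greenwood intervals for event-rate differences have no rule for sparse counts; they are near nominal at the background 12-month death and graft-loss rates but fail at early visits or when one arm's rate is near zero

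*Combined protocol and SAP*

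**What the plan says.** The methods are in Study Endpoints / Efficacy and Safety, section C (Additional Efficacy and Safety Variables for Evaluation). "For each efficacy event, simple event rate estimates (proportion of events) at 12 months will be obtained", and the two arms "will be compared using Z-statistic based, two-sided, 95% confidence interval" for RC − RE, where RC is the early-CNI control rate and RE the Thymoglobulin rate. For the composite and each of its components, Kaplan-Meier estimates are added: "Greenwood’s formula will be used to estimate standard errors and to derive the two-sided, 95% confidence interval of RC – RE, by visit window".

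These are the only between-arm methods stated for event outcomes. The text does not say whether the Z interval uses a pooled or an unpooled standard error. It gives no exact, score or other alternative for small counts, and no rule for an arm without events. No non-inferiority margin or decision rule is attached. The documents give no expected death, graft-loss or other event rates for this trial.

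**The concern.** A Z-based interval for a difference in proportions estimates its variance from the observed rates. When an arm has no events, the unpooled form gives that arm a variance of zero. When neither arm has an event, the pooled and unpooled forms both collapse to a point. Greenwood's formula behaves the same way: with no censoring before the time point it reduces to the binomial variance.

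The plan asks for these intervals at every visit window and for each component separately, so some comparisons will rest on very few events. The research hypothesis in the Synopsis includes similar subject and graft survival. An interval that is too narrow overstates how well the data support such a statement.

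**Working it through.** **Inputs from the documents**
- Allocation: subjects "will be randomly assigned to one of two Treatment Groups/Arms, in a 1:1 ratio, (55 subjects per Group/Arm"). Level: "A significance level of 5% and two-tailed tests were assumed for all testing".
- Dropout of 10% by month 12 (Number of Patients), leaving about 50 per arm.
- Background deaths: 4% (single-center series of 109, at least two months' follow-up); 9% in both groups (randomized steroid-free study); 6% versus 16% at one year (retrospective review of 63 recipients, control versus Thymoglobulin); 13% at 12 months (298-patient series, normal renal function).
- Background graft loss from the last three sources: 11% in both groups; 19% versus 32%; 21%.
- Left out: the abnormal-renal-function group of the 298-patient series, whose rates are higher.
- Early deaths: 4% at 1 month (298-patient series, normal renal function), or 0.04 × 55 = 2.2 per arm.
- A near-zero arm: dialysis at one year, 0.8% versus 13% (retrospective comparison of 118 and 80 patients, Overview of Thymoglobulin Safety).

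**Assumptions:** the rates 2% versus 4%, 1% versus 3%, and equal rates of 1% to 3%. The documents do not give them.

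**The plan's own figure.** Table 3's total of 110 (difference 0.32, SD 0.51 in both arms, 90% power) is reproduced by Welch power with the noncentral t distribution. The normal approximation gives 2 × (1.960 + 1.282)² × 0.51² / 0.32² = 53.4, so 54 per arm. The 55 per arm used below therefore stands.

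**Formulas**
- Unpooled Z: d ± 1.96 × √[p₁(1−p₁)/n + p₂(1−p₂)/n]
- Pooled Z: d ± 1.96 × √[2p̄(1−p̄)/n]
- Newcombe: Wilson limits for each arm, combined by square-and-add.
- Miettinen-Nurminen: all differences δ not rejected by the score test with the variance restricted to δ.

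Exact coverage is the sum, over all pairs of counts (x, y), of Bin(x; n, p₁) × Bin(y; n, p₂) for pairs whose interval contains p₁ − p₂.

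**Coverage at 55 per arm (%)**

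| Rates | Unpooled Z | Newcombe | Miettinen-Nurminen |
|---|---|---|---|
| 4% / 4% | 95.1 | 98.2 | 95.9 |
| 9% / 9% | 93.9 | 96.3 | 95.1 |
| 11% / 11% | 94.1 | 95.9 | 95.0 |
| 13% / 13% | 94.2 | 95.7 | 95.1 |
| 21% / 21% | 94.6 | 95.3 | 94.9 |
| 6% / 16% | 94.0 | 96.2 | 94.8 |
| 19% / 32% | 94.3 | 95.1 | 95.1 |
| 4% / 9% (two sources mixed) | 93.0 | 96.4 | 94.6 |
| 0.8% / 13% | 91.8 | 97.2 | 95.4 |
| 2% / 4% (assumed) | 88.5 | 98.2 | 96.5 |
| 1% / 3% (assumed) | 80.9 | 99.3 | 98.2 |

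Over all pairs of rates from 4% to 21%, the unpooled interval covers 93.0% to 95.1% at 55 per arm and 93.0% to 95.6% at 50. At 50 per arm, 0.8% / 13% gives 93.7% and 2% / 4% gives 86.4%.

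The pooled form does not rescue the sparse cases: 92.6%, 88.5% and 80.9% in the last three rows.

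At equal rates of 1%, 2% and 3% the unpooled interval covers 99.7%, 98.3% and 96.5%, which is conservative.

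**Degenerate and near-degenerate counts**
- 0/55 versus 0/55: Z interval [0, 0]; Newcombe ±6.5%, since 1.96²/(55 + 1.96²) = 3.84/58.84 = 6.5%. The chance of 0 versus 0 is (1−p)¹¹⁰: 33% at 1%, 11% at 2%, 0.4% at 5%, and under 0.01% at 9%.
- At 4% per arm, one given arm has no events with probability 0.96⁵⁵ = 10.6%, so at least one arm does with probability 1 − (1 − 0.106)² = 20%. At 0.8% the chance for that arm is 0.992⁵⁵ = 64%.
- 0/55 versus 4/55: −7.27% ± 1.96 × √(0.0727 × 0.9273/55) = −7.27% ± 6.86%, or [−14.1%, −0.4%]. This excludes zero, while Fisher's p = 0.118 and Newcombe gives [−17.3%, +0.6%]. Miettinen-Nurminen gives [−17.3%, −0.4%] and also excludes zero: the score statistic is 0.0727/√(2 × 0.0364 × 0.9636/55) = 2.04, times √(109/110) = 2.03. Fisher's test is itself conservative, so this example shows sensitivity to the method and does not prove an error by itself.

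**The case against.** A reader might infer that the intervals for death and graft loss at 12 months are the ones that fail, because such events are expected to be few. The documents do not support that. They state no expected counts, and their background rates correspond to about 2 to 18 events per arm (0.04 × 55 = 2.2; 0.32 × 55 = 17.6). At those rates the shortfall is at most about 2 points. Graft loss also includes death by the protocol's definition, so it cannot be the rarer event.

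A reader might also infer that the interval is always too narrow. It is not: with equal rates of 3% or less it is conservative.

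Three further points are fair. Calling the method Wald is an inference, because the text says only that it is Z-based; with a pooled standard error, coverage at equal rates of 4% to 21% is 94.9% to 95.9%. The cited dialysis rates do not belong to a listed endpoint, although renal replacement therapy counts as Stage 3 AKI, which is evaluated at month 3. Nothing is formally decided from these intervals.

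These points limit the scope and priority. They do not remove the gap: intervals are planned by visit window and by component, some will rest on very few events, and the stated method then undercovers when the rates differ and has zero width at 0 versus 0, whichever standard error is meant.

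**Conclusion.** The concern holds for sparse comparisons only. At the background death and graft-loss rates the planned interval is close to nominal (about 93% to 95%) and needs no correction for its own sake. At early visit windows, or where one arm's rate is near zero, coverage can fall to 91.8% (0.8% versus 13%), 88.5% (assumed 2% versus 4%) or 80.9% (assumed 1% versus 3%), and the interval vanishes when neither arm has an event.

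The calculations assume independent binomial counts with 55 per arm. They carry over to the Greenwood interval where there is no censoring before the visit. The 1% to 4% contrasts are illustrations, not rates the plan expects. The effect is on secondary and additional estimates, including how firmly similar patient and graft survival can be described. Priority is modest.

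**What to change.** In section C of the Study Endpoints, replace the Z-based interval with the Miettinen-Nurminen score interval for RC − RE. It stays closest to 95% across the rates tested above. Newcombe is an acceptable alternative and somewhat conservative; it is the choice if the team wants 0 versus 4 events not to exclude zero.

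For Kaplan-Meier differences by visit, compute log-log limits in each arm and combine them by square-and-add. State that an arm without events takes the score (Wilson) limit, since the log-log limit is undefined there.

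The cost is about one sentence and standard software, with no change to sample size or conduct. The downside is slightly wider intervals when events are rare: at 0/55 versus 4/55 the width rises from 13.7 points (14.1 − 0.4) to 16.9 with Miettinen-Nurminen (17.3 − 0.4) or 17.9 with Newcombe (17.3 + 0.6).
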